8. STATISTICAL CONSIDERATIONS

8.1 Summary

The key features of the trial are summarized in the following table (Table 1).

Table 1. Key Statistical features of the trial	
Feature	Description
Primary endpoint	COVID-19 7-point Ordinal Clinical Progression Outcomes Scale captured on study Day 15
Primary AIM	Assess if the treatment intervention improves the day 15 endpoint compared to the control arm
Sample size	1000 subjects
Inference approach	
The primary point of inference will be the likelihood ratio and corresponding support interval for the covariate adjusted treatment effect odds ratio. Likelihood ratios more extreme than 7 (or 1/7) will be interpreted as sufficient evidence to assert efficacy.
 
The odds ratio will be estimated with a cumulative probability ordinal regression model with logit link.

Planned Interim Analyses	There are 3 interim analyses for safety endpoints, and a final analysis of efficacy endpoints. The safety interim analyses will occur after 15 days of follow-up is completed for the first 150, 450, and 750 patients. The final analysis will occur after follow-up is complete for all enrolled subjects.
Planned Reporting Triggers	There are no planned reporting triggers.
Planned stopping rules	At each interim analysis, the difference in mortality risk will be calculated, and the one-sided hypothesis that mortality risk in the intervention arm exceeds the mortality risk in placebo will be compared to the null hypothesis of equal mortality risk. The trial will be stopped if the likelihood ratio exceeds the threshold listed below.
Type I error rate	The combination of a 1/7 likelihood ratio threshold and the safety stopping rule result in a simulated type I error rate of 0.02
Power	The minimal detectable effect at 80% power is 0.73

8.2 Planned interim analyses for mortality

At each interim analysis, the difference in mortality risk will be calculated, and the one-sided hypothesis that mortality risk in the intervention arm exceeds the mortality risk in placebo will be compared to the null hypothesis of equal mortality risk. The trial will be stopped if the likelihood ratio exceeds the threshold listed below. Generally, the level of evidence required to stop a study for safety concerns is less than the level of evidence required to assert efficacy of the intervention. Likewise, there is not the same level of concern for type 1 error control for safety outcomes as there is for efficacy endpoints; however, the threshold values were selected so that the trial-wise risk of ending early for mortality is 0.1 if the treatment is equivalent to placebo. To provide context for the LR thresholds listed in the table below, we have also provided α_N , the p-value threshold which approximates the LR threshold if the p-value were calculated from a likelihood ratio test.

N	LR Threshold	α_N
150	6.3	0.0275
450	4.0	0.0479
750	3.3	0.0612

8.3 Analysis plan for primary endpoints

The statistical analysis plan (SAP) contains a more complete description of analysis methods, definitions, and sensitivity analyses. In this section, we reprint relevant portions of the SAP.

The data from the clinical trial will be analyzed after follow-up is completed for all study subjects. The analysis will be intent-to-treat, meaning that patients will be analyzed according to the randomization schedule regardless of the treatment administered. The key result of the analysis is an estimate of the treatment effect odds ratio, its likelihood ratio when compared to the null, and the corresponding 1/7 likelihood support interval, all of which will be estimated from a cumulative probability ordinal regression model (CPM) with logit link. The marginal likelihood function for the treatment effect parameter will be the asymptotic regression coefficient distribution; specifically, it will be the normal distribution density function with mean and standard deviation equal to the regression estimates. Likelihood ratios more extreme than 7 will be interpreted as sufficient evidence to assert efficacy. In order to increase study power, the following variable will also be included into the regression:

1. Treatment (1 parameter)
2. Age (2 parameters, restricted cubic spline)
3. Sex (1 parameter)
4. SOFA score (1 parameter, linear term)
5. Baseline COVID-19 7-point Ordinal Clinical Progression Outcomes Scale score (possible range:3-6) (2 parameters, quadratic)
6. Time from symptom onset in days (2 parameter, non-linear term)
7. Site indicator variables (either as a main effect or as a random effect, depending on the number of sites enrolling patients)

8.3.1 Model fit

Model fit will be assessed with probability scale residuals and with leave-one-out diagnostics like DFBETAS. If model diagnostics indicate that an alternative link function provides a superior fit, then supplementary information will be sent to the DSMB to decide if an alternative link function should be used.

8.3.2 Missing data

We anticipate rare or no missingness for data points during a patients in-hospital course. There may be missing data for the COVID-19 7-point Ordinal Clinical Progression Outcomes Scale score after hospital discharge, which relies on phone follow-up. After discharge, distinguishing between category 1 and category 2 on the scale requires speaking to the participant or surrogate about normal daily activities. If the patient is not reached for follow-up phone calls after discharge, the COVID-19 7-point Ordinal Clinical Progression Outcomes Scale score will be classified as category 2 (not hospitalized, but unable to resume normal activities). If the patient is reached for a follow-up call post-charge and reports category 1, this classification of category 1 will be carried forward to future follow-up calls if the patient cannot be reached. For example, if the patient cannot be reached for the Day 8, 15, or 29 follow-up calls, a category 2 score will be reported for all three visits. If the patient is successfully contacted on the Day 8 call and reports category 1, and then the patient cannot be reached for a Day 15 call, the category 1 score from Day 8 will be carried forward to Day 15.

Missing data for a covariate used in the primary model will be multiply imputed using predictive mean matching if number of observations missing covariate values exceeds 5 percent. If fewer than 5% of observations have missing covariate values, missing values will be imputed with a single conditional mean.

8.3.3 Assertion of efficacy

Likelihood ratios more extreme than 7 (or 1/7) will be interpreted as sufficient evidence to assert efficacy.

8.4 Trial characteristics

8.4.1 Inference

Decision making using the likelihood approach in a clinical trial centers on three quantities: the point estimate of the treatment effect (an odds ratio, for example), a corresponding interval estimate, and a single number summary that measures the relative evidence for one hypothesis compared to another. These three quantities are not unlike the point estimate, 95% confidence interval, and p-value that are generated in frequentist analyses. In fact, the point estimates are often identical, and the interval estimates are often similar. The LR and the p-value, however, are distinct measures of evidence. The LR is a ratio: the density of the trial data if the treatment works (alternative hypothesis) divided by the density of the trial data if the treatment does not work (null hypothesis). A LR of 1 indicates the data are neutral; neither hypothesis is supported over the other. Large LR are evidence in support of the treatment working while small LR are evidence in support of the null. In short, the LR level of evidence is based on comparing the likelihood of the data under two competing models – the alternative hypothesis and the null hypothesis. This is different to using a p-value as the level of evidence because the p-value essentially compares what actually happened in the trial to what might have happened in the trial if it were repeated infinitely and the null hypothesis were true. Because it is impossible to compute what might have happened if the rules for decision making are not fully predefined, using a p-value for decision making is not well suited for a trial like this one in which DSMB requests and pandemic circumstances prompt design changes. The LR approach on the other hand, is based on a relative likelihood of observed outcomes under two competing models at the same point in time making it especially appropriate for settings where pre-specification of the timing or frequency of sequential analyses is not possible.

Even though the LR (instead of the p-value) is the quantity of primary interest for decision making, the analysis plan does control type 1 error. Sequential likelihood ratio tests of two prespecified hypotheses have a natural bound on type 1 error of $1/k$ where k is the threshold for asserting efficacy. In this study, the combination of the stopping rule for mortality and the large number of subjects accrued before the first analysis for efficacy result in a bound-on type 1 error well within traditional levels of 0.05.

[figure not shown]
8.4.2 Type I error rate and power

The long-run operating characteristics were estimated by generating study data to reflect different treatment effect sizes. The simulated study dataset was evaluated according to the stopping rule and analysis plan described above. For each effect size, 1000 simulated datasets were analyzed. A Type I error occurred if the study asserted efficacy when in fact there was no treatment effect. The Type I error rate was calculated as the proportion of null-effect studies in which the error occurred. A Type II error occurred if the study failed to assert efficacy when there was a beneficial treatment effect. For each treatment effect, power was calculated as the proportion of studies that did not result in a Type II error.

The study endpoint for control subjects was simulated to match the outcomes in the control arm of a recent clinical trial.³ In each simulation setting, the distribution for the treatment arm was calculated by adjusting the control arm outcome distribution according to the setting-specific treatment effect size and data generation model.

The figure below is the estimated power curve for the trial design (Figure 1).

Figure 1. Power of the trial assuming enrollment of 1000 participants.

8.5 Analysis plan for additional analyses of the primary endpoint

8.5.1 Quantification of effect of donor plasma characteristics on treatment efficacy

The impact of the antibody levels and neutralization activity of the donor plasma on the primary endpoint will be estimated with ordinal regression models. The models will include the same covariates listed for the primary endpoint analysis, except the treatment assignment variable will be replaced with either (a) a measure of donor plasma antibody level or (b) a measure of donor plasma neutralization. Both variables will be included in models as a restricted cubic spline in order to capture potential non-linear associations with the outcome.

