3.3 Study Design

We will conduct a multi-site, investigator-initiated, blinded, placebo-controlled, randomized clinical trial evaluating convalescent donor plasma for the treatment of adults hospitalized with COVID-19. Plasma will be collected and distributed to sites through blood donation groups partnering with Vanderbilt University Medical Center (VUMC)'s blood donation center partner. Anti-SARS-CoV-2 antibody quantification assays will be completed on donor plasma at VUMC prior to plasma distribution. Only plasma with antibody quantification above the neutralizing threshold will be used in the trial.

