5.2 Convalescent Plasma Group

Patients randomized to the active treatment arm will receive a single dose of 1 unit (200-399 ml) of convalescent plasma infused intravenously per site institutional policy governing blood product transfusions. Convalescent plasma used in this trial will be ABO compatible with the participant's blood type. The convalescent plasma will be supplied to enrolling sites for the trial. Quantitative SARS-CoV-2 antibody testing will be completed at Vanderbilt University Medical Center on convalescent plasma used in the trial. Plasma that is believed to be neutralizing will be used in this trial and will be prioritized based on neutralizing capabilities. Only plasma that contains anti-SARS-CoV-2 antibodies at a level above the threshold for neutralization will be used in the trial.

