The trial will be stopped if the likelihood ratio exceeds the threshold listed below. Generally, the level of evidence required to stop a study for safety concerns is less than the level of evidence required to assert efficacy of the intervention. Likewise, there is not the same level of concern for type 1 error control for safety outcomes as there is for efficacy endpoints; however, the threshold values were selected so that the trial-wise risk of ending early for mortality is 0.1 if the treatment is equivalent to placebo ($\Delta = 0$). To provide context for the LR thresholds listed in the table below, we have also provided α_N , the p-value threshold which approximates the LR threshold if the p-value were calculated from a likelihood ratio test.

N	LR Threshold	α_N
150	6.3	0.0275
450	4.0	0.0479
750	3.3	0.0612

3. Analysis plan for primary endpoint

The data from the clinical trial will be analyzed after follow-up and data lock is completed for all study subjects. The analysis will be intent-to-treat, meaning that patients will be analyzed according to the randomization schedule regardless of the treatment administered. The main result will be an estimate of the treatment effect odds ratio, its likelihood ratio when compared to the null, and the corresponding 1/7 likelihood support interval, all of which will be estimated from a cumulative probability ordinal regression model (CPM) with logit link. The marginal likelihood function for the treatment effect parameter will be the asymptotic regression coefficient distribution; specifically, it will be the normal distribution density function with mean and standard deviation equal to the regression estimates. Likelihood ratios more extreme than 7 will be interpreted as sufficient evidence to assert efficacy. In order to increase study power, the following variables will also be included into the regression:

1. Treatment (1 parameter)
2. Age (2 parameters, restricted cubic spline)
3. Sex (1 parameter)
4. Baseline SOFA score (1 parameter, linear term)
5. Baseline COVID-19 7-point Ordinal Clinical Progression Outcomes Scale score (possible range:3-6) (2 parameters, quadratic)
6. Time from symptom onset in days (2 parameter, non-linear term)
7. Site indicator variables (either as a main effect or as a random effect, depending on the number of sites enrolling patients)

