5.1 Quantification of donor plasma efficacy

Quantification of donor plasma efficacy. The impact of the binding and neutralization levels of the donor plasma on the primary endpoint will be estimated with two ordinal regression models. In the first, the model will include the same covariates listed for the primary endpoint analysis with the addition of a measure of donor plasma binding level. Similarly, in the second model, a measure of donor plasma

neutralization levels will be added to the models. The variables will be included into the models as a restricted cubic spline with three knots in order to capture potential non-linear associations with the outcome. For observations in the control arm, binding and neutralization values will be set to zero.

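### Protocol 8.5.1 drops the treatment term from the donor-titre model and SAP 5.1 keeps it; with controls at zero, the protocol version largely re-tests plasma versus placebo

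*Protocol*

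**What the plan says.** Below, titre stands for either donor measure (antibody or binding level, or neutralization).

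- **Protocol 8.5.1** takes the primary-model covariates, "except the treatment assignment variable will be replaced with either (a) a measure of donor plasma antibody level" or a neutralization measure. On form it says "Both variables will be included in models as a restricted cubic spline". It gives no number of knots and no value for control patients, and does not say whether controls are in the model.
- **SAP 5.1** describes a pair of models. For binding, it says that "the model will include the same covariates listed for the primary endpoint analysis with the addition of a measure of donor plasma binding level"; the other does the same with neutralization. It specifies three knots and adds: "For observations in the control arm, binding and neutralization values will be set to zero".
- **SAP section 3** lists the primary-model variables. Item 1 is "Treatment (1 parameter"), so adding titre to that list keeps treatment in the model.
- **Protocol 8.3** points to the SAP as the fuller description and says "In this section, we reprint relevant portions of the SAP".
- **Protocol 3.3** says of the product: "Only plasma with antibody quantification above the neutralizing threshold will be used in the trial". Protocol 5.2 repeats the restriction.

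Neither document gives knot locations, the scale on which titre enters, or a rule for judging this analysis.

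**The concern.** The two documents specify different models for the same analysis, and no text says which prevails. The analysis is meant to show whether the antibody content of the plasma matters for efficacy. That is a question about variation among recipients.

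Replacing treatment by titre most naturally means that titre stands in for treatment across both arms. The only control value in either document is zero, and every plasma unit is above a threshold. The titre variable then separates the arms, and with treatment absent its terms absorb the overall plasma effect. A benefit of plasma that is the same at every titre could be reported as a titre effect. Depending on scale and spread, the fitted curve could also show a gradient among recipients that does not exist. An analyst could follow either text, and could choose between them after seeing results.

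**Working it through.** **1. Does titre stand in for arm?** Take equal arms, controls at 0, and plasma titre with mean m and SD s. Then Cov(arm, titre) = m/4, Var(arm) = 1/4 and Var(titre) = s²/2 + m²/4. With CV = s/m, this gives R² = 1/(1 + 2CV²). The documents give no titre spread, so a range of CV is shown. The spline column is numerical (three knots at plasma-arm quantiles, lognormal titre).

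| Titre CV | R² with arm, linear titre | R² with arm, spline |
|---|---|---|
| 0.25 | 1/1.125 = 0.89 | 0.97 |
| 0.5 | 1/1.5 = 0.67 | 0.91 |
| 1.0 | 1/3 = 0.33 | 0.75 |
| 1.5 | 1/5.5 = 0.18 | 0.63 |

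**2. Setting for the simulations.** From the documents: N = 1000, 500 per arm, OR 0.73 (the effect stated to have 80% power). They give no figure for the titre analysis itself, so there is none to reproduce. The stated power can be checked approximately with the proportional-odds formula: power = Φ(|ln 0.73| × √(N(1 − Σp³)/12) − z). With LR 7, z = √(2 ln 7) = 1.973. If 1 − Σp³ = 0.96, power = Φ(0.315 × √80 − 1.973) = Φ(0.84) = 0.80. The category distribution is not in the documents, so 0.96 is an assumption; over 0.90 to 0.98, power is 0.77 to 0.81.

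Other assumptions for step 3: control distribution (0.20, 0.35, 0.05, 0.15, 0.07, 0.08, 0.10), no other covariates, knots at the 10th, 50th and 90th plasma-arm percentiles, controls at 0, and **no** effect of titre among recipients. Proportional-odds maximum-likelihood fits, 1000 trials per setting. The 5% level is a yardstick, since the plan sets no rule.

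**3. Results at OR 0.73** (proportion of trials significant, treatment replaced / kept).

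| Titre as entered | Overall 2-df titre test | 90th vs 10th percentile contrast | Mean false OR, replaced | SE ratio, kept/replaced |
|---|---|---|---|---|
| Raw, log-SD 0.3 | 0.664 / 0.032 | 0.060 / 0.039 | 0.92 | 1.40 |
| Raw, log-SD 0.5 | 0.626 / 0.058 | 0.206 / 0.066 | 0.87 | 1.63 |
| Raw, log-SD 0.8 | 0.576 / 0.049 | 0.499 / 0.057 | 0.79 | 1.74 |
| Raw, log-SD 0.8, truncated at half the untruncated median | 0.632 / 0.047 | 0.450 / 0.034 | 0.82 | 1.92 |
| Log scale, SD 0.8 | 0.684 / 0.050 | 0.043 / 0.048 | 0.98 | 1.15 |

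The true high-versus-low OR is 1 throughout. At OR 0.9 the overall test rejects in 0.109-0.121 of trials with treatment replaced and 0.038-0.060 with it kept.

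**4. Independent repeat.** A different assumed outcome distribution, titre CV 0.25 to 1.5, and 400 trials per setting gave 52-66% with treatment replaced, 4-7% with it kept, and 3-8% in recipients only. With no plasma effect (CV 0.5 and 1.0) the replaced model rejected in 3-4%, so the excess comes from plasma versus placebo. With an average OR of 1 and a real slope of −0.15 log-odds per SD of log titre, the replaced model detected it in 19-23% of trials and the kept model in 34-36%. The protocol version can therefore miss a real gradient as well as suggest a false one.

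**5. Does the control value matter?** In one dataset, controls were moved from 0 to the plasma median. With treatment kept, the titre likelihood-ratio statistic stayed at 2.421, because the treatment term absorbs any constant. With treatment replaced, it moved from 3.442 to 2.702.

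**The case against.** **The criticised model combines two texts.** The protocol drops treatment but gives no control coding; the SAP sets controls to zero but keeps treatment. If the protocol meant recipients only, treatment would be constant and rightly omitted, and the model would test dose-response; a recipients-only 2-df test rejected in 4.6-5.7% of trials. This reading is open, so the re-test finding is conditional. But the protocol does not state it, and replacing the treatment variable is more naturally read as covering both arms.

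**The 58-68% is not an error rate for a planned test.** The protocol says only that the impact will be estimated. With controls at zero and plasma effective, outcomes do differ between zero and positive titre, so the rejection is correct for that null. This stands as a matter of definition. The harm is in reading the result as evidence about antibody content, which is the purpose the section states.

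**The false gradient among recipients depends on unknown facts.** It is 4% on the log scale and 6% at raw log-SD 0.3. The largest figures (50%, mean OR 0.79) come from a setting without a threshold; with one they are 45% and 0.82. This stands, and the whole range should be quoted.

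**The threshold is only part of the mechanism.** Truncation moved the overall test only from 0.576 to 0.632. The spread of titre relative to its mean matters more.

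**The SAP already has the sounder model.** Protocol 8.3 points readers to it, and the reprint sentence sits in 8.3, so its reach to 8.5 is arguable. That makes the correction easy, but no text says the SAP prevails.

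**Conclusion.** The concern holds. The replace-versus-add conflict is explicit in the current text of both documents and needs no assumption. The consequence is conditional on fitting the protocol model to both arms with controls at zero. On that reading, with a plasma OR of 0.73 and no gradient among recipients, the titre terms are significant in 58-68% of trials, against 3-6% with treatment kept. The false contrast among recipients ranges from 4% to 50%, against 3-7%. These sizes rest on assumed outcome and titre distributions and on models without the other covariates. A second assumed control distribution in a rank-score check (2000 trials per setting) gave similar figures for the replaced model: 57-70% overall and 6-47% for the contrast.

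This is an additional analysis, so the primary inference is untouched. It should still be corrected, because the protocol rule as written can give a wrong answer to the question it poses. The missing knot locations and titre scale alone would be only gaps in detail.

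**What to change.** 1. Change Protocol 8.5.1 to match SAP 5.1: keep the treatment indicator, add titre, and state which patients are included and one constant value for controls.
2. State in both documents that the three knots are set from plasma-arm titres only, and on which scale titre enters. Half the sample sits at the control value, so whole-sample quantile knots would fall at or near zero.
3. State that the titre question is judged by the titre terms given treatment, or equivalently in purpose by a fit among plasma recipients only.
4. Note that, with controls at zero, the treatment coefficient in this model is an extrapolation to zero titre, outside the range of plasma used, and is not the overall treatment effect. Centring titre at the plasma-arm median would make it interpretable; this is optional and does not change the titre test.

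The cost is wording in Protocol 8.5.1 and one sentence in SAP 5.1. The titre effect will look less precise: the standard error of the 90th-versus-10th-percentile contrast was 1.15 to 1.92 times as large with treatment kept. The precision given up came from the plasma-versus-placebo contrast, not from titre differences among recipients.
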